**10.2. Proposed Analysis**

Statistical analysis will be performed to assess homogeneity of the study groups and efficacy of treatment. The primary outcome will use chi-squared test (with or without continuity correction). The secondary outcome will be assessed using independent T test if normally distributed or Mann-Whitney test if not.

The difference between the two groups will be significant if the p values are less than 0.05.

The analysis will be performed by [name] who is a Clinical Specialist on the Arthrex Research team based in Germany.

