##### **3. Intervention – clinic visit 1 or 2**

- a) Check understanding and continuing desire to participate in study if 2nd visit.
- b) Complete consent form.
- c) Patient fills out a PEM score and demographics collected on SOS.
- d) Randomisation.
- e) If in PRP group 15ml blood sample taken with Arthrex ACP double syringe and processed (see processing instructions in Appendix.9).
- f) Aspiration.
- g) If in PRP group - Injection of PRP (the same volume as aspirated).
- h) Pressure dressing with gauze, wool and crepe for 48 hours.

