## **8. DATA COLLECTION AND MANAGEMENT**

### **8.1. Data Collection**

Data will be collected as both electronic files and paper questionnaires and letters. Electronic files will be collected with the Surgical Outcomes System, a research registry run by Arthrex. All data will be kept secure and confidential, see appendix 11. Paper files will be kept in a locker filing cabinet in the Upper Limb Unit Secretaries office.

All participants will be assigned a unique identifier for the duration of the study. A separate log will be kept linking the ID number to the participant which will be kept and stored confidentially.

Surgical outcome system is an online bespoke database containing the data as shown on the case report forms in Appendix 6 and 7. Patients will be identified only by their unique study ID and demographic information (age at time of study and sex) will be entered. Access is password protected on an individual basis. The database is a Microsoft SQL Server database using transparent data encryption. Plausibility data validation is in place, data is checked upon saving. There is a daily full back up of the data. Data enquires will be handled by Miss [name].

SOS is hosted on servers operated exclusively for Arthrex by Amazon Web Services, Inc. (AWS). The data will be stored on an AWS Server in Germany. The data centre has multiple layers of operational and physical security to ensure the integrity and safety of the data. The data centre utilizes state-of-the-art electronic surveillance and multi-factor access control systems. The data centre is staffed 24 / 7 by trained security guards and access is authorized on a least privileged basis. See also appendix 11. An anonymised database will be stored on secure shared NHS Grampian drive, with access only to research team.

Data files from SOS will be extracted onto NHS computers as password protected excel files will be stored on secure shared NHS Grampian drive, with access only to research team.

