**10. STATISTICS AND DATA ANALYSIS**

**10.1. Sample Size Calculation**

90 participants in each arm would give a 90% power to detect a change in recurrence rate of 25%. We believe this is adequate as current recurrence rates are 59%. This would need to be increased to 100 participants recruited per arm to allow for 10% drop out from follow-up.

As the recurrent rate is so large recruiting 90 patients would detect up to a 25% difference in recurrence rate. To ensure the trial is not extended beyond the point of answering our question we have also calculated numbers to allow for the trial to be closed early if we have sufficient data.

62 participants completing follow-up in each arm would give 90% power to detect a change in recurrence rate of 30%. This would need to be increased to 69 per arm to allow for 10% drop out from follow-up.

46 participants completing follow-up in each arm would give 90% power to detect a change in recurrence rate of 35%. This would need to be increased to 51 per arm to allow for 10% drop out from follow-up.

Therefore we will undertake initial data analysis after 51 and 69 participants have completed their 6 week review and if the difference in the recurrence rate is more than 35% or 30% then we will conclude the trial, but all outstanding follow up will be completed and data included in final analysis.

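### Section 10.2 appears to test baseline homogeneity of randomised groups and leaves age, sex and baseline PEM out of the recurrence comparison: a small efficiency and reporting point

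*Combined protocol and SAP*

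**What the plan says.** Section 10.2 opens: "Statistical analysis will be performed to assess homogeneity of the study groups and efficacy of treatment". It names no variable, no test for homogeneity, and no consequence if the groups differ. Recurrence is then compared by a chi-squared test, with the continuity correction left open and no covariate. The section's only decision rule is: "The difference between the two groups will be significant if the p values are less than 0.05".

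Baseline data are available. In section 3.1, step 3, before the randomisation step: "Patient fills out a PEM score and demographics collected on SOS". Section 8.1 says which demographics: "demographic information (age at time of study and sex) will be entered". The hand-health profile in Appendix 2 has 11 items.

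Section 6.1 randomises 1:1 in blocks and states no stratification factor. No section uses age, sex or baseline PEM in the recurrence comparison.

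**The concern.** Under proper randomisation, baseline differences between arms arise by chance, so the null hypothesis of a baseline significance test is already known to be true. A small p value is a false alarm. A large one does not show that an imbalance is harmless, because what matters is how strongly the variable predicts the outcome. The plan has no rule for either result, so any adjustment would be chosen after the data had been seen. Section 10.2 gives the analysis to a member of the research team of the company that funds the study and supplies the device, which makes a rule fixed in advance more useful.

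Baseline data already in hand could instead enter the recurrence comparison through a prespecified model. If they predict recurrence, the treatment difference is estimated more precisely at no cost in patients.

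**Working it through.** **Inputs.** From section 10.1: 59% recurrence with current treatment, a 25-point change (so 34% with PRP), 90% power and 90 completers per arm. From section 10.2: alpha 0.05, taken as two-sided because that reproduces the plan's figures. The documents do not say how strongly age, sex or PEM predicts recurrence, so the share of variation explained (R²) is assumed.

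**1. The plan's own sample size.** With mean proportion (0.59 + 0.34)/2 = 0.465:

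- Uncorrected: m = [1.960 √(2 × 0.465 × 0.535) + 1.282 √(0.59 × 0.41 + 0.34 × 0.66)]² / 0.25² = (1.3825 + 0.8751)² / 0.0625 = 81.6, or 82 per arm.
- Continuity-corrected: (m/4) × [1 + √(1 + 4/(m × 0.25))]² = 20.39 × 2.0937² = 89.4, or 90 per arm.

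The same formula gives 62 per arm for 30 points and 46 for 35 points, as stated. The point therefore leaves the sample size untouched.

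**2. False alarms, if homogeneity is judged at p < 0.05.** With k independent tests the chance of at least one is 1 − 0.95^k.

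- Age, sex and PEM total (k = 3): 1 − 0.8574 = 14.3%.
- Age, sex and the 11 hand-health items separately (k = 13): 48.7%. The items are probably correlated, so treat this as a ceiling.

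**3. Power gained by adjusting recurrence.** To a good approximation the variance falls by the factor (1 − R²), so 90 per arm is worth 90/(1 − R²). Power without continuity correction is Φ{[0.25 √n − 1.3825] / 0.6829}.

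| Assumed R² | Effective n per arm | Power | Gain (points) |
|---|---|---|---|
| 0 | 90.0 | 92.6% | 0 |
| 0.02 | 91.8 | 93.1% | 0.5 |
| 0.05 | 94.7 | 93.8% | 1.2 |
| 0.10 | 100.0 | 94.9% | 2.3 |

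A simulation (90 per arm, 59% v 34%, one covariate, 1,500 trials per setting) agrees. The variance of the standardised risk difference relative to the unadjusted one was 1.01 with no association, 0.94 at R² = 0.054 and 0.88 at R² = 0.121. Power, taken from the treatment coefficient of the logistic model, went from 93.3% to 94.3% and from 91.9% to 94.9% in the last two settings.

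**4. Error control of the adjusted analysis.** This was simulated with equal recurrence in both arms and covariates that predict nothing.

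- *13 covariates (each hand item entered separately), uncorrected robust standard error:* type I error about 7 to 8% at 90 per arm and 8 to 11% at 46 per arm.
- *Three covariates, uncorrected:* 5.5% and 6.3%.
- *Three covariates, small-sample correction:* about 5% and 6%.

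The number of covariates and the correction therefore both matter.

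**The case against.** The strongest reply is that nothing is wrong with the primary test. An unadjusted chi-squared test is valid under 1:1 randomisation, its error rate already allows for chance imbalance, and no stratification factor calls for adjustment. That stands.

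The opening sentence of 10.2 also does not commit the trial to baseline p values. A descriptive comparison would fit the words, and the 0.05 rule follows the two outcome tests. That stands too: significance testing is the natural reading but remains an inference, and the 14% depends on it and on the three variables assumed.

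No section says that age, sex or PEM predicts recurrence, so the gain may be nil. This is correct, and the range in the working starts at zero.

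A reader might infer that the baseline data serve no other purpose. The documents do not support that. The secondary objective in 2.1.2 asks whether treatment alters the PEM score, which suggests some use of baseline PEM. Adjusting the PEM comparison for its own baseline could well gain more than adjusting recurrence, but that is a separate matter.

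Finally, a careless adjustment could do harm. The type I error figures for 13 covariates bear this out, and the fix is limited accordingly.

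**Conclusion.** The point holds as a minor improvement in efficiency and reporting. Section 10.2 should not invite baseline significance tests, and it leaves baseline data out of the recurrence comparison that could cheaply be used there.

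The gain is none if the covariates do not predict recurrence, and about 1 to 3 percentage points of power at the planned 25-point difference if they explain 5 to 10% of its variation. That range is an assumption, and power at 90 per arm is already about 93% without the continuity correction.

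Two stronger readings should be resisted. One is that the planned comparison is biased or underpowered: it is valid, and 90, 62 and 46 per arm all reproduce. The other is that the plan throws away substantial power: the documents give no prognostic strength from which such a loss could be shown.

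**What to change.** In 10.2, drop the homogeneity wording and add text along these lines:

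> Baseline characteristics will be tabulated by arm without significance tests. Recurrence will be compared as a risk difference, standardised to the analysed participants from a logistic model with treatment, age, sex and the total baseline PEM hand-health score. The 95% confidence interval will use a robust variance with a small-sample correction. The unadjusted chi-squared test will be reported alongside. These covariates are fixed and will not change in the light of the baseline table.

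The model takes three covariates only, with the 11 hand-health items as one total. The text should also state how that total is formed, how a missing baseline score is handled, and which of the two analyses carries the primary conclusion. The early-closure looks in 10.1 keep using the raw difference in recurrence, so they need no change.

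The cost is a few lines of wording and slightly more analysis work, with no new data and no more patients. The one downside is a small inflation of type I error if the small-sample correction is left out. If a descriptive table was all that was meant by homogeneity, the first sentence of the new text settles it.

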**10.3. Missing Data**

Any patients with missing all follow up data will be deemed to have not completed follow up and will be excluded with a withdrawal form completed. If partial follow up data is available we will use this in analysis.

**10.4. Transfer of Data**

There is no plan for patient identifiable data to be transferred between collaborators, de-identified data could be sent via NHSmail to other NHSmail accounts. All analysis will be performed on secure password protected computers with data extracted from Surgical Outcomes System. All data is de-identified – see appendix 11. This is a single site study.

**11. TRIAL/STUDY MANAGEMENT AND OVERSIGHT ARRANGEMENTS**

**11.1. Trial/Study Management Group**

The trial/study will be co-ordinated by [name], [name] and Miss [name]. They will form the trial steering committee (TSC). [name] as Chief Investigator, [name] is an Orthopaedic Consultant experienced in research and Miss [name] as Principle Investigator. The TSC will meet annually and operate as per sponsors SOP.

**11.2. Trial/Study Management**

Miss [name] will oversee the study and will be accountable to [name]. The Clinical Research Fellow/Orthopaedic registrar/Research Nurse will be responsible for checking the CRFs for completeness, plausibility and consistency. However, this remains the overall responsibility of the CI. Any queries will be resolved by the CI or delegated member of the study team.

A study-specific Delegation Log will be prepared for the site, detailing the responsibilities of each member of staff working on the study.

**12. INSPECTION OF RECORDS**

The CI, PIs and all institutions involved in the study will permit study related monitoring, audits, and REC review. The CI agrees to allow the Sponsor or, representatives of the Sponsor, direct access to all study records and source documentation.

**13. GOOD CLINICAL PRACTICE****13.1. Ethical Conduct of the Study**

The study will be conducted in accordance with the principles of good clinical practice (GCP).

In addition to Sponsorship approval, a favorable ethical opinion will be obtained from the appropriate REC and appropriate NHS R&D approval(s) will be obtained prior to commencement of the study.

**13.1.1 Confidentiality**

All evaluation forms, reports, and other records will be identified in a manner designed to maintain participant confidentiality. Patient CRFs will only contain study specific data and study identification.

All paper records will be kept in a secure storage area with limited access to study staff only. Anonymised patient data (written on case report forms) will be stored in a locked filing cabinet in the Upper Limb Unit Secretaries office, which is itself secured. Only the research team will have access to this data.

Electronic records will be stored in Arthrex Surgical Outcomes System (SOS). SOS is hosted on servers operated exclusively for Arthrex by Amazon Web Services, Inc. (AWS). The servers are located in a data centre in Virginia, United States, until 2018 when SOS will be separated into two systems, EMEA and USA. EMEA data will then be stored on an AWS Server in Germany. The data centre has multiple layers of operational and physical security to ensure the integrity and safety of the data. The data centre utilizes state-of-the-art electronic surveillance and multi-factor access control systems. The data centre is staffed 24 / 7 by trained security guards and access is authorized on a least privileged basis. See also appendix 11.

Data files from SOS will be extracted onto NHS computers as password protected excel files will be stored on secure shared NHS Grampian drive, with access only to research team.

Clinical information will not be released without the written permission of the participant, except as necessary for monitoring and auditing by the Sponsor or its designee. The CI and study staff involved with this study will not disclose or use for any purpose other than performance of the study, any data, record, or other unpublished, confidential information disclosed to those individuals for the purpose of the study. Prior written agreement from the Sponsor or its designee will be obtained for the disclosure of any said confidential information to other parties.

This study will be using a specially designed outcomes portfolio and as such our data will not be available for global comparison.

The investigator will keep a record of the study ID to enable his research team to track patients involved in the study.

### **13.1.2 Data Protection**

The CI and study staff involved with this project will comply with the requirements of the General Data Protection Regulations (GDPR) and the Data Protection Act 2018. The HRA recommended wording to fulfil transparency requirements under the GDPR for health and care **research** has been included in the PIS.

The CI and study staff will also adhere, if appropriate, to the current version of the NHS Scotland Code of Practice on Protecting Patient Confidentiality. Access to collated participant data will be restricted to the CI and appropriate study staff.

Computers used to collate the data will have limited access measures via user names and passwords.

Published results will not contain any personal data that could allow identification of individual participants.

### **13.1.3 Insurance and Indemnity**

The NHS Grampian Health Board and The University of Aberdeen are Co-Sponsoring the study.

**Insurance:** Grampian Health Board will maintain its membership of the Clinical Negligence and Other Risks Insurance Scheme (“CNORIS”) which covers the legal liability of Grampian in relation to the study].

**Indemnity:** The Sponsors do not provide study participants with indemnity in relation to participation in the Study but has insurance for legal liability as described above.

## **14. STUDY CONDUCT RESPONSIBILITIES**

### **14.1. Protocol Amendments, Deviations and Breaches**

The CI will seek approval for any amendments to the Protocol or other study documents from the Sponsor, REC and NHS R&D Office. Amendments to the protocol or other study docs will not be implemented without these approvals.

In the event that a CI needs to deviate from the protocol, the nature of and reasons for the deviation will be recorded in the CRF, documented and submitted to the Sponsor. If this necessitates a subsequent protocol amendment, this will be submitted to the Sponsor for approval and then to the appropriate REC and lead NHS R&D Office for review and approval.

In the event that a serious breach of GCP is suspected, this will be reported to the Sponsor immediately using the form “Breach Report Form”.

**14.2. Study Record Retention**

Archiving of study documents will be maintained for 7 years, in accordance with the sponsors archiving SOP and the documents will be stored off site using the dedicated NHSG achieve by Removal Services Scotland. After this time they will be securely disposed of. De-identified data will be available on SOS unless a patient or user unsubscribes, the study will be unsubscribed after 7 years and the data deleted.

**14.3. End of Study**

The end of study is defined as last patient last visit (LPLV). The Sponsor, CI and/or the TSC have the right at any time to terminate the study for clinical or administrative reasons.

The end of the study will be reported to the Sponsor and REC within 90 days, or 15 days if the study is terminated prematurely. The CI will ensure that any appropriate follow up is arranged for all participants.

A summary report of the study will be provided to the Sponsor and REC within 1 year of the end of the study

**15. REPORTING, PUBLICATIONS AND NOTIFICATION OF RESULTS**

**15.1. Authorship Policy**

Ownership of the data arising from this study resides with the study team and their respective employers. On completion of the study, the study data will be analyzed and tabulated, and a clinical study report will be prepared.

**15.2. Publication**

The clinical study report will be used for publication and presentation at scientific meetings. Investigators have the right to publish orally or in writing the results of the study.

Summaries of results will also be made available to Investigators for dissemination within their clinical areas (where appropriate and according to their discretion).

**15.3. Peer Review**

Internal peer review has been undertaken by [name], Consultant Orthopaedic Surgeon and [name], Research Nurse. The study was also reviewed by Arthrex during the funding application.

**16.**

**FUNDING and EQUIPMENT**

Arthrex, an orthopaedic medical device company, is providing funding in the form of supply of disposable material and research support. They will provide up to 100 units of the ACP double syringe. This is used to collect the blood sample, process the PRP and inject the PRP into the ganglion (see Appendix 3). The processing is performed by a centrifuge, provided by Arthrex, in the Orthopaedic out-patient department. This is already in place. Arthrex provide indemnity for the centrifuge (Indemnity number MIA No: 310/13). Both the ACP double syringe and the centrifuge are already in use in NHS Grampian. PRP injections are currently performed for other conditions i.e. Tennis Elbow and Achilles Tendonitis.

Research support will be provided in the form of data management via SOS and statistical support and final analysis.

There are no other additional costs out with the usual treatment costs.

## APPENDIX 2: Patient Reported Measure

## **PATIENT EVALUATED MEASURE SCORE (PEMS)**

## **Part 1 – Treatment:**

Please put a circle around the number that is closest to the way you feel about how things have been for you. There are no right or wrong answers.

**1. Throughout my treatment I have seen the same doctor:**

**2. When the doctor saw me, he or she knew about my case:**

**3. When I was with the doctor, her or she gave me the chance to talk:**

1	2	3	4	5	6	7
As much as I wanted				Not at all		

**4. When I did talk to the doctor, he or she listened and understood me:**

**5. I was given information about my treatment and prognosis:**

1	2	3	4	5	6	7
All that I wanted						Not at all

## Part two – How is your hand now?

## Hand Health Profile

## **1. The feeling in my hand is now:**

**2. When my hand is cold and/or damp, the pain is now:**

**3. Most of the time , the pain in my hand is now:**

**4. The duration my pain is present is:**

1	2	3	4	5	6	7
Never						All the time

## 5. When I try to use my hand for fiddly things, it is now:

## **6. General, when I move my hand it is:**

1	2	3	4	5	6	7
Flexible						Stiff

## 7. The grip in my hand is now:

A horizontal scale with seven points labeled 1 through 7. The first point is labeled "Strong" and the last point is labeled "Weak".

**8. For everyday activities, my hand is now:**

1	2	3	4	5	6	7
No problem				Useless		

## 9. For work, my hand is now:

1	2	3	4	5	6	7
No problem				Useless		

**10. When I look at the appearance of my hand now, I feel:**

1      2      3      4      5      6      7  
Unconcerned      Embarrassed & self-conscious

## **11. Generally, when I think about my hand I feel:**

1	2	3	4	5	6	7
Unconcerned				Very upset		

### 3. Bearing in mind my original condition, I feel my hand is now:

1      2      3      4      5      6      7  
Better than expected      Worse than expected

### APPENDIX 3: Processing Procedure for PRP

#### Arthrex ACP® Double Syringe

Accessories: Double syringe, red cap, anticoagulant, centrifuge specimen mesocaps, countercaps, bucket, countercapweight (2 optional), countercapweight, 10 ml ABS-1022B + sleeve ABS-10225-15 or countercap, 15 ml ABS-10227. Optional: sterile cup for intraoperative application. A separation under sterile conditions is possible, bucket can be sterilized.

Prior to withdrawing, tighten the inner syringe (turn it clockwise) and push both plungers forward until the stop.  
Optional: Withdraw approximately 1.5 ml anticoagulant into the syringe.  
Caution: Draw back only the plunger of the outer syringe – red marking!  
Note: If the ACP is injected within 30 minutes after withdrawing, the use of anticoagulant is not important.

Withdraw approximately 35 ml of venous blood and seal the syringe with the red cap.  
Note: Only pull the outer plunger of the outer syringe – red marking!

Gently rotate the syringes in order to mix the blood and the anticoagulant.

Place the syringe into one bucket and an appropriate countercapweight in the opposite bucket. Under sterile conditions place the double syringe in the sterilized bucket and an appropriate countercapweight in the opposite bucket (2 optional, countercapweight, 10 ml ABS-10226 + sleeve ABS-10225-15 or, countercapweight 15 ml ABS-10227).

Turn the centrifuge at 1300 rpm for 5 minutes.  
Remove the syringe holding care to keep it in an upright position to avoid mixing.

In order to transfer the supernatant (ACP) from the large outer syringe into the small inner syringe, slowly push down on the outer syringe while slowly pulling out the plunger of the small inner syringe.

[figure not shown]

Discard the small inner syringe and place a needle on it. The ACP is ready for use at the point of care.  
Optional: Transfer the ACP in a sterile cup for intraoperative usage.

Arthrex GmbH | [name]  
[contact] | [contact] | [www.arthrex.com](http://www.arthrex.com)  
© 2013, Arthrex Inc. All rights reserved. LA015-005 Rev. G

